10. ETHICAL CONSIDERATIONS

a. Regulation statement

This study will be conducted according to the principles of the Declaration of Helsinki (version 64, Fortaleza, 2013) and in accordance with the Medical Research Involving Human Subjects Act (WMO).

b. Recruitment and consent

Patients will be recruited in sixteen physiotherapy practices within a 12 month time period. All patients are consecutive patients that meet the inclusion criteria of this study, either referred to physiotherapy by a physician or contacting a physiotherapist by direct access because of mobility problems. Initial information on the study will be given by the secretary of the physiotherapy practice. The secretary will also give an information letter to the potential participants. The investigator of this study and an independent contact person can be approached for questions. The potential participant will get the time he/she needs to think about participation with a maximum of one week. However, it is recommended to commence as soon as possible considering the perceived need for treatment. The researcher will subsequently make an appointment with the participant for the first assessment and will also deal with informed consent. The data of the repeated measurements of the tests on the four assessments (0-, 3-, 6- and 12 months) will be used. Not all patients in this study are

followed for the full duration of this study. From those older adults not eligible based on the in- and exclusion criteria, only clinical data is analysed.

c. Objection by minors or incapacitated subjects

Older adults suffering from mild dementia are eligible to be included in the study as well. Guardians and/or (family) care givers are asked to sign a modified informed consent with strict arrangements when to withdraw the participant. These arrangements are conform Code of Conduct: Incapacitated Elderly.

d. Benefits and risks assessment, group relatedness

The risk of participating can be considered negligible and in the earlier studies it appeared clear that older adults like to participate and that the burden is minimal. Included patients are referred to physiotherapy and they receive physiotherapy. Physiotherapy is no invasive therapy and the risk of adverse events can be considered very small. The choice to include older adults suffering from mild dementia as well, was made to ensure a representative sample of current physiotherapeutic practice in the Netherlands. Dementia will not be diagnosed as part of the study, but when it is present (i.e., as diagnosed by a specialist during the regular treatment trajectory separate from the study) these patients will not be excluded. After all, community-dwelling, older adults with dementia are referred to primary care physiotherapy regularly. To study the effect of Coach2Move in this group, separate subgroup analyses will be carried out.

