For patients included during these 15 months, we will collect data at baseline, directly after the end of the program and 6 and 12 months after the start of intervention. In this stepped wedge study, we have set our measurement periods at time intervals of three months, resulting in a total inclusion duration of 15 months, an implementation period of 3 months and a follow-up of 12 months (thus clinical study duration 30 months in total). At the start of the study, all clusters start together in the control group, where none of the practices work according to the Coach2Move strategy and provide usual care. At different time points the clusters will cross-over to the intervention condition. The time points at which the different practices transition to Coach2Move are determined at random. By the end of the trial, all practices will have implemented Coach2Move.

The Implementation and Wash-out period consists of 3 months in which the therapists retrieve a 2-day education in Coach2Move and in which 3 peer assessment meetings take place. During this period, no measurements are carried out to give the therapists the opportunity to gain experience with Coach2Move before the measurements commence in the intervention period. This has no direct consequences for the participants.

All data will be collected by researchers from Radboudumc. Data sampled at baseline relevant for clinical decision-making will be communicated to the PT(G), to avoid load on the patient.

Figure 1. Depiction of proposed stepped wedge, cluster randomised design.

	3 months	6 months	9 months	12 months	15 months	18 months
Group 1 (Practices 1,2,3,4)	Control	Imp + WO	Intervention	Intervention	Intervention	Intervention
Group 2 (Practices 5,6,7,8)	Control	Control	Imp + WO	Intervention	Intervention	Intervention
Group 3 (Practices 9,10,11,12)	Control	Control	Control	Imp+ WO	Intervention	Intervention
Group 4 (Practices 13,14,15,16)	Control	Control	Control	Control	Imp+ WO	Intervention

Abbreviations: Imp +WO = Implementation and wash-out period.

A mixed methods process evaluation is designed to investigate the processes through which the Coach2Move intervention operates on outcomes and how the implementation of the program is achieved in the context of potential organisational and other differences between regions and practices.

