Quantitative data will be collected and qualitative analyses (open interviews, focus groups and surveys) will be held with the participating PT(G)'s, relevant stakeholders and patients. Hindering and facilitating factors found during analysis will be used to fine-tune the implementation of the intervention strategy.

To test fidelity quality indicators are scored by reviewing patient files of physiotherapists.

This will be done by two independent blinded persons. Random sampling of patient files of different time periods after implementation will be compared with files from the control period. Subject to review is the change in scores between and after implementation of Coach2Move.

Time schedule:

July 2017 – October 2017	Development of implementation tools: educational materials, ICT optimization per practice, preparation measurement economic evaluation, development of measurement instruments for process evaluation, and randomisation of start points, meeting with the patient advising group to reflect on educational material and measurements. Publication of the trial protocol and the process analysis protocol.
November 2017 – March 2019	Gathering of data and measurements of actual usual care and care based on the Coach2Move approach and experiences with the implementation by professionals and patients.
November 2017 – March 2020	Control- and intervention measurements over 4 clusters: inclusion of patients, quality indicator measurement (clinical reasoning, patient-centeredness and monitoring by measurements), measurement of primary and secondary outcomes on pre-post and at 6- and 12 months follow-up.
March 2020 – December 2020	Finalizing analyses and publications.

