6. STUDY POPULATION

a. Population (base)

Sixteen PT practices will participate. All practices comprise at least two physiotherapists of whom at least one is specialized in geriatrics, as evidenced by a professional degree.

During the study, data will be collected from community-dwelling older adults (≥ 70 years) who visit the PT practice due to mobility problems related to activities of daily living. In addition, potential participants must have a sedentary lifestyle or must be at risk of losing an active lifestyle in the near future (as rated by the participant, relatives, or a referring physician).

b. Inclusion criteria

All older adults from 70 years or older who are referred to the physiotherapist are included in this study. However, not all older adults will be followed for the full duration of the study. Only those who are community-dwelling, have mobility related problems or problems related to activities of daily living and have a sedentary lifestyle or are at risk of losing an active lifestyle in the near future are eligible for follow-up. Only clinical data is obtained from the participants who are not eligible for follow-up to control for selection bias.

Eligible for separate analysis:

- Patients with problems understanding advises and/or communicating with the professional due to Dutch language problems and/or mild dementia are not excluded, because we think that the Coach2Move approach will be adequate because of the focus on contextual resources.

c. Exclusion criteria

A potential subject who meets any of the following criteria will be excluded from participation in this study:

- Patients who are not ambulatory after treatment and/or are in palliative phase.
- Patients who are indicated to become institutionalised in the near future.

d. Sample size calculation

Primary endpoints are TUG and LAPAQ at 6 months, and the combined objective of this trial is to show that one of these improves while the other does not deteriorates [13]. With the Stepped Wedge design as below (4 groups of 4 practices with 5 patients in each of 5 measurement periods and none in the implementation period, so 400 patients in total), a simulation study shows that the SE (standard error) is $0.21 \times SD$ for each endpoint when the ICC = 0.10 (regardless of the size of the effect due to the linearity of the analysis model).

Figure 1. Depiction of proposed stepped-wedge, cluster randomized design.						
	3 months	6 months	9 months	12 months	15 months	18 months

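### Section 10.b gives 12 months for recruitment, but the stepped-wedge design needs 18 calendar months; stopping at 12 would leave half the practices without a single intervention patient

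*Combined protocol and SAP*

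**What the plan says.** - **Section 10.b (Recruitment and consent):** "Patients will be recruited in sixteen physiotherapy practices within a 12 month time period".
- **Section 4 (Study design):** each period of the wedge lasts three months. The section describes this as "resulting in a total inclusion duration of 15 months, an implementation period of 3 months and a follow-up of 12 months". Its own sum of these three parts is 30 months.
- **Figure 1:** six three-month columns, ending at month 18. Group 3 is in implementation and wash-out in months 10-12 and enters the intervention in month 13. Group 4 is in control up to month 12, in implementation in months 13-15, and has its only intervention period in months 16-18.
- **Section 6.d (Sample size):** "4 groups of 4 practices with 5 patients in each of 5 measurement periods and none in the implementation period", 400 patients in total. Section 4 expects about 200 per condition.
- **Time schedule (section 4):** one row, "November 2017 – March 2019", covers data gathering under usual care and Coach2Move. Another, "November 2017 – March 2020", covers both the enrolment of patients and the follow-up measurements.
- **Implementation period:** three months in section 1, in one part of section 4 and in Figure 1. Another part of section 4 plans four months per cluster, one of them for wash-out.

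**The concern.** The recruitment window tells practices and the ethics committee when enrolment closes. In a stepped wedge, control time comes first, so an early close removes intervention patients only, and it removes most from the groups that cross over last. Section 7.c says that every practice serves as its own control. A practice with no intervention patients cannot do that. At stake are the planned 400 patients, the roughly equal split, and the within-practice comparison in Groups 3 and 4.

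**Working it through.** **1. Length of the design.** Section 4: 15 + 3 = 18 calendar months to the end of enrolment, and 18 + 12 = 30 months in total. Figure 1 agrees: 6 periods x 3 months = 18.

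**2. Patients by group.** Each open group-period holds 4 practices x 5 patients = 20 (section 6.d). Implementation cells hold none.

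| | Control | Intervention, to month 18 | Intervention, to month 12 |
|---|---|---|---|
| Group 1 | 20 | 80 | 40 |
| Group 2 | 40 | 60 | 20 |
| Group 3 | 60 | 40 | 0 |
| Group 4 | 80 | 20 | 0 |
| Total | 200 | 200 | 60 |

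The full design reproduces the plan's 400 patients, 200 and 200. Closing at month 12 leaves 200 + 60 = 260. The two zeros follow from Figure 1 alone. The 60 depends on the planned 5 per practice per period.

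**3. Another reading of the 12 months.** If it meant 12 enrolling months per practice, each group would fill its first four open periods. Intervention patients would be 60 + 40 + 20 + 0 = 120, with 200 controls, so 320 in total. Group 4 would still supply no intervention patients.

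**4. Standard error.** Model: fixed period effects, random practice intercept, ICC 0.10, implementation cells left out. For each practice, in units of SD squared, V = 0.10 J + (0.90/5) I over its open periods. The SE is the square root of the treatment element of the inverse of the sum of X'V^-1 X over the 16 practices.

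- Full design: 0.213 SD (the plan states 0.21).
- Closed at month 12: 0.225 SD.

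**5. Power.** Section 6.d inputs: TUG effect 1.4/2.0 = 0.70 SD, margin 0.4/2.0 = 0.20 SD; LAPAQ effect 15/30 = 0.50 SD, margin 5/30 = 0.167 SD; correlation of the estimates +0.3. Let A be TUG superior with LAPAQ non-inferior, and B the reverse. Power = P(A) + P(B) - P(A and B), from a bivariate normal. No alpha is stated, so a range is shown. With SE 0.21 and one-sided alpha 0.025 the result is 85.8%, which reproduces the plan's 86%.

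| One-sided alpha (assumed) | Full, SE 0.213 | Month 12, SE 0.225 |
|---|---|---|
| 0.05 | 91.4% | 88.3% |
| 0.025 | 84.6% | 79.9% |
| 0.0125 | 75.9% | 69.9% |

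Scaled to the plan's SE, the month-12 value is 0.21 x 0.2248/0.2132 = 0.221. At alpha 0.025 power then falls from 85.8% to 81.3%.

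**6. Time schedule.** Counting both end months, November 2017 to March 2020 is 2 + 12 + 12 + 3 = 29 months, against the stated 30. November 2017 to March 2019 is 2 + 12 + 3 = 17, against 18.

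**The case against.** **The patient numbers are conditional.** Section 4 asks for at least 25 patients per practice. If practices reached 25 within 12 months, spread evenly over their open periods, there would be 300 control and 100 intervention patients, with an SE of 0.190 SD and power of 92% (alpha 0.025). This stands: the 60 and the power loss hold only at the planned pace. It does not rescue Groups 3 and 4, which still supply no intervention patients.

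**The power loss is modest.** This stands too. A reader might set 80% against the plan's 86%, but that compares two different standard errors. Like for like, the fall is about 5 points, and scaled to the plan's SE power stays just above 80%.

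**The calendar sets no recruitment limit.** A reader might infer a 17-month limit from the time schedule. The documents do not state one: the row that names inclusion runs to March 2020 and also holds the follow-up. The rows give no days, so the gap could be smaller than a month. Even if the last month of enrolment were lost (80/3, about 27 intervention patients), the SE would move only from 0.213 to 0.215 SD and power from 84.6% to 83.8%.

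**Follow-up is not cut by a shorter window.** A reader might infer that closing recruitment at 12 months also damages the 12-month follow-up. It would leave more time for it. Only the one-month calendar gap bears on follow-up, and the 6-month endpoints used for the sample size fall well inside the calendar.

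**Conclusion.** The 12 months in section 10.b contradict section 4 and Figure 1, and neither reading tried above reconciles them. With a close at calendar month 12, Groups 3 and 4 (8 of 16 practices) supply no intervention patients; this needs no assumption about recruitment rate. They would not be empty, since 60 and 80 controls remain at the planned pace.

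At 5 patients per practice per period, 260 of 400 patients are enrolled, 200 control and 60 intervention. Power falls from about 85% to 80%, given ICC 0.10, a random practice intercept, correlation +0.3 and the assumed one-sided alpha of 0.025. The main harm is structural: half the practices lose their within-practice comparison.

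The calendar gap is minor. Some 12-month visits of patients enrolled in the final month could fall after March 2020, which would touch the last assessment and the cost-utility horizon.

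**What to change.** 1. Reconcile the length of the implementation period first. Section 4 gives both three and four months, while section 1 and Figure 1 give three. The 18 and 30 months rest on three; with four and the same 15 enrolling months they become 15 + 4 = 19 and 19 + 12 = 31.
2. If three months is confirmed, replace the 12 months in section 10.b with 18 calendar months, of which 15 are enrolling months in each practice, in line with section 4 and Figure 1.
3. On the same basis, extend the time-schedule rows by one month, to April 2019 and April 2020.

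The cost is a few words of protocol text and one month on the calendar. With three months confirmed, design, sample size and analysis do not change.
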